## **Safety Analysis**

Safety evaluations will be performed by recording clinical adverse events at the time originally reported, and they will be followed at regular intervals until resolution. Adverse events will be provided in data listings.

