### Secondary Objectives:

- To evaluate treatment effect of Vector on overall quality of life
- To evaluate treatment effect of Vector on sleep quality
- To evaluate treatment effect of Vector on physical activity levels
- To Evaluate treatment effect of Vector on Ventilator collected parameters
- To Evaluate treatment effect differences on nocturnal SpO2 and PaCO2 or TcCO2

**Endpoints:**Primary Endpoint:

Daytime CO2 levels at the end of 4-6 weeks of therapy as determined by Arterial Blood Gas (PaCO2)

Secondary Endpoints:

- Average daily device usage
- Therapy Comfort and Preference
- Incidence of Unanticipated Serious Adverse Device Effects (USADEs) and Serious Adverse Events (SAEs) for the Vector vs. the control group.

Exploratory Endpoints:

- Changes in quality of life scores ((CAT) SGRQ, dyspnea ratings mMRC),
- Ventilator collected parameter differences after 6 weeks of use (Respiratory Rate (RR), Minute Ventilation (MV))
- Sleep Quality differences as measured by PSG and actigraphy
- Changes in activity levels (mean and max activity counts)

**Study Population:** Approximately 30 COPD patients with chronic hypercapnia and evidence of expiratory flow limitation will be included.  
**Phase:** Pilot study

**Sites/Facilities Enrolling Participants:** Temple University Hospital

**Description of Study Intervention:** NIV with Auto Adjusting EPAP

**Study Duration:** Approximately 12 months

**Participant Duration:** Approximately 15 weeks

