### **Secondary Endpoints:**

1. Average 30-day Ventilator Usage hours
2. Patient Comfort and Therapy Preference based questionnaire responses

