### **Exploratory Endpoints:**

1. Other Ventilator Parameters
  - a. Respiratory Rate
  - b. Minute Ventilation
  - c. % flow limited breaths
  - d. Patient ventilation synchrony
2. Total therapy Titration Time
3. Screening session parameters
  - a. % flow limited breaths
  - b. Delta Xrs final screening value
4. Quality of Life Questionnaire
5. Activity (measured via the Actiwatch)
6. Reported Adverse Events
7. Sleep Quality
  - a. Total Sleep Time
  - b. Sleep Efficiency
  - c. Sleep Stage distribution
  - d. Arousal and awakening indices
  - e. Nocturnal TcO2 variability

[figure not shown]
- f. Nocturnal TcO2 averages
- g. Nocturnal SpO2 Saturation

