### **Adverse Event Assessment and Follow-Up**

Adverse events will be collected on an ongoing basis following signing of informed consent. Detailed information regarding the event will be recorded on the appropriate form in the electronic case report form (eCRF), where the Investigator will determine the severity of the event, relationship to study product (assessed only by those with the training and authority to make a diagnosis), and time of resolution/stabilization of the event. Follow-up data to ascertain the existence of residual effects from the event will be obtained. Serious adverse events must be reported to the sponsor within 24 hours of discovering the occurrence of the SAE. The research staff is required to complete and submit the sponsor's standard SAE form detailing the event.

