### **General Considerations**

The primary analysis will be performed including all consented participants. Descriptive data tables will be provided for all variables of interest. Continuous data will be presented by mean, standard deviation, median, minimum, and maximum observation. Data will be presented in the untransformed and transformed format (if applicable) for each continuous variable. Categorical data will be presented as frequencies and percentages. All formal statistical analyses will be performed using either SAS® or SPSS® software. Significance tests will be conducted at a two-sided significance level of  $p < 0.05$ .

There are no statistical criteria for terminating the study. No sensitivity analysis will be completed, and any deviations to the original statistical plan will be noted in the analysis report.

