## **Primary Analysis**

Since this was a crossover study, the endpoints were compared between the two therapies as paired samples. For each continuous endpoint, the paired differences will be examined for normality using the Shapiro-Wilk and Kolmogorov-Smirnov tests, and if the distribution does not deviate significantly from normality, the treatment effect will be examined using a paired t-test; otherwise, the endpoint was examined using the non-parametric Wilcoxon Signed-Ranks test. Categorical data will be evaluated using the McNemar Test.

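### The plan states a Vector-versus-control comparison of SAE and USADE incidence but does not specify it: the safety output is listings only, and no rule assigns events to a therapy period

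*Combined protocol and SAP*

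**What the plan says.** **Status of the endpoint.** The Protocol Synopsis lists among its secondary endpoints "Incidence of Unanticipated Serious Adverse Device Effects (USADEs) and Serious Adverse Events (SAEs) for the Vector vs. the control group". Section IV carries the same item as a secondary objective. Section IV's own secondary endpoints are only two: ventilator usage hours, and "Patient Comfort and Therapy Preference based questionnaire responses". Adverse events appear in Section IV as exploratory endpoint 6, "Reported Adverse Events".

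**Analysis.** The Safety Analysis paragraph of Section XI names one output: "Adverse events will be provided in data listings". Elsewhere in Section XI, Primary Analysis states that "the endpoints were compared between the two therapies as paired samples" and that "Categorical data will be evaluated using the McNemar Test". General Considerations adds that "Categorical data will be presented as frequencies and percentages".

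**Collection.** Section IX, Adverse Event Assessment and Follow-Up, states: "Adverse events will be collected on an ongoing basis following signing of informed consent". The Device Deficiencies text of Section IX says that onset and duration are collected. The Safety Analysis paragraph says that events are recorded when first reported.

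**Exposure.** Section V gives each randomized period 4 to 6 weeks. NIV-naïve participants (Cohort 2) first use the device at home for 2 weeks on SOC settings, and Visit 2 falls 14 to 16 days after Visit 1. Those randomized to SOC first then continue the same use. SOC therapy is delivered on the Vector device with the Vector therapy switched off.

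**The concern.** A listing shows individual events. It gives no numerator by therapy, no denominator and no interval, so the named output does not deliver the stated comparison. Whoever writes the report would have to settle several questions after seeing the data: which date places an event in a period, what happens to events before randomization, who is in the denominator, and whether the endpoint is secondary or exploratory.

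This matters even in a pilot. Section XVII says the data may support regulatory clearance, Section XI says they may be used to power a pivotal trial, and Section VII says there is no DSMB. A comparative safety statement from this trial should not rest on choices made after the fact.

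**Working it through.** The plan has no figure to reproduce: it gives no power analysis, expected event rate or safety margin. The check is of the text first, then of exposure.

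**1. Do the general rules fill the gap?** McNemar's test needs a yes or no for each participant under each therapy. Four things needed to build that are absent or unclear:
- No section assigns an event to Vector, SOC or the time before randomization.
- Two dates are in play (onset, and first report), and the plan does not say which governs. An event that starts in period 1 but is reported after crossover could go to either therapy.
- Section IX defines an adverse device effect by its relation to the investigational device. Both therapies run on that device, so device-relatedness cannot separate them; therapy mode can.
- The only analysis population named is all consented participants, which includes people who never receive randomized therapy.

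**2. Whom would a paired test lose?** Under Withdrawal (Section VI), participants may be discontinued because of adverse events or a further admission for a COPD exacerbation. An inpatient admission meets Section IX's definition of serious. A period-1 SAE can therefore remove the participant from the pairs. The same section expects about 50 enrolled for 30 completing, so at most 50 − 30 = 20 could lack a pair. How many of these would leave after randomization is not given.

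**3. How informative would the test be?** With d discordant participants all in one direction, the exact two-sided p is 2 × 0.5^d. For d = 5 this is 0.0625; for d = 6 it is 0.031. At least six one-directional discordant participants are needed for p < 0.05.

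**4. Exposure in Cohort 2 if acclimation events were counted as SOC.** Ratio = (SOC weeks + 2) / Vector weeks.

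| SOC period (weeks) | Vector period (weeks) | Randomized periods only | With acclimation added to SOC |
|---|---|---|---|
| 4 | 4 | 4/4 = 1.00 | 6/4 = 1.50 |
| 6 | 6 | 6/6 = 1.00 | 8/6 = 1.33 |
| 4 | 6 | 4/6 = 0.67 | 6/6 = 1.00 |
| 6 | 4 | 6/4 = 1.50 | 8/4 = 2.00 |

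With a 16-day acclimation (16/7 = 2.29 weeks), the two equal-period ratios become 6.29/4 = 1.57 and 8.29/6 = 1.38. At an equal weekly event rate and equal periods, SOC would collect 6/10 = 60% or 8/14 = 57% of Cohort 2 events instead of 50%.

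**5. Trial-wide.** The documents do not give Cohort 2's share f, so it is assumed. With equal periods of p weeks, ratio = (p + 2f)/p:
- f = 25%: 1.08 (p = 6) to 1.13 (p = 4)
- f = 50%: 1.17 to 1.25
- f = 75%: 1.25 to 1.38

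The third column of the table shows that exposure can differ in either direction, in either cohort, even without acclimation. Person-time is therefore needed in any case.

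**The case against.** The strongest reply is that the plan already covers the comparison. If SAE incidence is an endpoint, the paired rule applies to it, McNemar's test is named for categorical data, tables of counts and percentages are promised, and onset dates allow assignment to periods. Much of this stands. A reader might infer that the comparison cannot be made, or that the trial will yield no Vector-versus-SOC safety result; the documents do not support that. What the general rules leave open is how events are assigned and who is counted, and the one paragraph devoted to safety does not invoke them.

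A reader might also infer that SOC will carry extra exposure and make Vector look safer than it is. That does not follow either. Acclimation precedes randomization, and the plan is silent on those events; it does not count them as SOC. The bias arises only if someone later does so. Nor is an excess of 33% to 50% a trial-wide figure: it holds for Cohort 2 with equal periods.

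Finally, it could be argued that the synopsis settles the endpoint as secondary. The revision history records that endpoints were clarified in revision 3.0, but nothing shows whether the synopsis or Section IV reflects the intent. The documents support reconciling the two, not choosing one.

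**Conclusion.** The point holds as a gap in specification. A comparative SAE/USADE item is stated twice, its status is inconsistent between the synopsis and Section IV, and the named safety output does not produce it. The general paired rule is a possible route, but it lacks an assignment rule and can drop the very participants whose first-period SAE led them to stop.

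The exposure imbalance is conditional on counting acclimation events as SOC. On that condition it is 1.33 to 1.50 in Cohort 2 with equal periods and 1.00 to 2.00 across unequal periods within the 4-to-6-week range. The pooled ratio is smaller and rests on an assumed cohort share. These ratios assume that participants complete both periods and a 2-week acclimation. The change is worth making before analysis.

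**What to change.** - Assign each event by onset date to one of three categories: pre-randomization (including acclimation), SOC mode or Vector mode. Define the last two by therapy mode, not by device.
- Add a descriptive table by therapy giving participants with any AE, SAE, ADE and USADE, event counts, person-weeks, and exact two-sided 95% confidence intervals for the proportions. Include every participant who received randomized therapy, even for one period only.
- Show acclimation events separately.
- Keep the listings, and treat any McNemar test of SAE incidence as supportive only.
- Reconcile the endpoint's status across the synopsis and Section IV's secondary objectives, secondary endpoints and exploratory endpoints.

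The cost is one added table and SAP wording. No new data are needed, provided the onset date is captured for every adverse event, as the Device Deficiencies text of Section IX indicates.

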## **Missing Data**

It is not anticipated that imputation methods will be necessary in this study.

## **Interim Analysis**

Since this is a pilot study, descriptive statistics may be reviewed as the study is ongoing, but formal statistical comparisons will be performed after the study is completed.

## **XII. Direct Access to Source Data / Documents**

Only site clinical study staff and approved Philips staff working with the research will know the identity of the participants. All information recorded by the study team and provided for analysis will be given a study ID number. A unique source record will be available for each study participant and will include informed consent review process, HIPAA completion (as applicable), medical history, and concomitant medications.

Privacy rules and requirements according to federal and state governing regulations will be implemented. All the information collected as part of this study will be kept confidential. All information collected for this study will be kept in a secured area or stored in a password protected computer if digital. Except when required by law, participants will not be identified by name, social security number, address, telephone number, or any other direct personal identifier in study records. For records disclosed to Philips participants will be assigned a unique code number.

Results of the study related data, medical history, and information obtained from the questionnaire and device data will be reported and received by Philips. Philips will use participant study data for research purposes to support engineering objectives described in this protocol.

In addition, participant records may be reviewed in order to meet federal and state regulations. Reviewers may include representatives from the FDA or similar government authorities in other countries where the device is being used, and Philips for the purposes of the following side effects, and to gather additional information related to the study, and the Institutional Review Board (IRB). Participant permission for review of confidential information is granted by signing the associated informed consent. Philips will ensure that it follows all applicable state and federal data protection regulations.

## **A. Provisions to Protect the Privacy Interests of Participants:**

Participants will only interact with approved members of the research staff and will have the option to decline to provide any information that they are uncomfortable revealing. All research staff (site and sponsor) will receive training regarding the protection of human subject data. Participant's medical records will only be accessed after obtaining written consent from the participant and will only be reviewed by members of the research staff for whom review of this information is necessary for continued participation in the study (e.g. Philips research staff and study investigator reviewing the medical records). Participant identifiers, other than study ID number must be redacted in date before sending to sponsor.

## **B. Case Report Forms**

Study related case report forms (CRF's) and source documentation will be collected and maintained by the sponsor, will be kept confidential, and stored in a secure location if on paper or on a secure server or protected device. Only staff delegated by the PI will have the ability to enter in, or make changes to, the CRF's and source documents.

## **XIII. Quality Control and Quality Assurance**

The PI and study personnel will be trained to the study protocol, study product, TMF documents, monitoring plan, CRFs and/or eCRFs, direct data reporting, and all Sponsor expectations, as applicable. Once complete, training and delegations will be documented for PI and study personnel.

Data queries will be addressed by delegated study personnel and CRF/ eCRFs will be reviewed and signed off by PI prior to study closure. Monitoring will be completed in accordance with US CFR, ICH-E6 GCP Section 6, and ISO 14155:2011 as applicable.

## **XIV. Ethics**

This study will be submitted and reviewed by the Western Institutional Review Board. All participants will be consented prior to completing the trial. The Primary Investigator will review all adverse events as it relates to the study device.

All data will be kept confidential and in a secure location if on paper or on a secure server or device. Only approved study personnel will have access to study related documents. All electronic data shall be stored in a coded data set. All paper documents shall be kept in a secure area. Study data and source will be made available for study related monitoring or audits by the IRB/IEC, sponsor, or regulatory inspection(s). Results of the study related data, and information obtained from the engineering study, will be collected, received and reported by Philips. Philips will use participant study data for research purposes to support scientific and marketing objectives described in this protocol.

## **XV. Data Handling and Recordkeeping**

Hard copies of the study will be kept on site for at least 2 years after study completion. The sponsor will maintain study records indefinitely. Records will be stored at Iron Mountain, a secure information management services company.

## **XVI. Financing and Insurance**

If the participant is injured during the course of the trial and as a direct result of this trial, they should contact the Principal Investigator, [name]. The participant will be directed to seek clinically appropriate medical care for that injury. However, we cannot guarantee that the medical care and treatment will be provided without charge or that it will be paid for by the participant's insurance company, and the costs incurred may ultimately be the participant's responsibility.

## **XVII. Registration on ClinicalTrials.gov or other applicable registry**

This trial will be registered on Clinical Trials.gov. It is the intent that these data may be used for to support regulatory clearance and/or consideration for a submission to peer review publication.

## **XVIII. Risk and Benefit Analysis**

### **A. Potential Risks and Discomforts**

Adverse effects of NPPV are usually minor and manageable. The masks may cause some discomfort and air pressure and flow have adverse effects. All adverse effects encountered, including mask discomfort, nasal or mouth congestion or dryness, eye irritation, gastric insufflation, and nasal bridge ulceration will be recorded on data sheets that are part of the case report form.

The risks of using the Vector NIV Device are minimal. Use with the NPPV devices may cause a decrease in the inability to adequately clear secretions, an increased risk for aspiration of gastric contents, increase in symptoms of sinusitis or otitis media, and decrease in blood pressure. These are minimal risks of using the device and should they occur during the course of the study, they be recorded. Other more serious adverse effects, such as pneumothorax or aspiration pneumonia, are distinctly unusual

in the outpatient setting, but will be recorded if they occur. Significant adverse events will be reported to the Institutional Review Board. Patients currently on NIV may find Vector to be less comfortable than their previous NIV, but this is not a real medical risk.

Arterial blood gas determinations are part and parcel of routine pulmonary function testing and are performed by trained respiratory therapists on a daily basis. The blood gas draws as part of this study is consistent with usual care in initiating NIV. The research technician will employ the usual precautions while performing such a procedure by employing adequate aseptic technique. The arterial blood gas sampling test can cause pain, tenderness or swelling at the puncture site and possibly bleeding, local infection, lightheadedness or fainting.

Standard PSG (sleep study) risks might include: complaints of skin irritation from the adhesives or tapes used to secure the electrodes and any necessary skin preparation.

Participants may also find some of the chemical adhesive smells offensive. The participant may sleep poorly.

The patient may sleep poorly during the nocturnal sleep study and thus may be sleepy the next day. If the patient is too sleepy to drive home, other forms of transportation will be utilized.

COVID-19 is a risk with any in-person activity, but proper mitigation strategies, including COVID-19 screening, disinfection, and other site safety procedures, will be implemented to minimize patient risk.

Thus, we believe that although there may be discomforts associated with the use of this device and study related procedures, the risks are minimal.

## **B. Potential Benefits**

Although participation in this trial will not result in any direct benefit to the subject, they will be contributing to generalizable data that will help improve device design and function

## **C. Compensation for Research-Related Activities**

Participants will only be compensated for the activities that they complete. Participants' payment will be in the form of a Gift card/Clinicard according to the following schedule.

For taking part in this research, participants may be paid up to a total of \$750.00 or \$800.00 as per the schedule below:

Visit Number	Amount
Visit 1	\$50.00 (\$100 for Naïve only)
Visit 2	\$100.00
Visit 3	\$300.00
Visit 4	\$300.00
TOTAL	\$750.00 (\$800 for Naïve only)

#### **D. Publication**

It is the intent that these data will be used/considered for a submission to peer review publication, white paper or scientific abstract

## Appendices

### Appendix A

#### VECTOR TITRATION PROTOCOL

Device titration will take approximately 3 hours. There will be 2 separate Titration periods. The Vector Auto EPAP will be titrated in both fixed pressure and using AVAPS that will auto titrate Pressure Support based up on a set tidal volume. Each titration session will last approximately 1.5 hours. Prior to the initiation of the device titration, a baseline TCO2, SPO2, Respiratory Rate will be recorded. If existing NIV user, the device titration initial pressure setting will start at their current device pressure settings.

Immediately prior to conducting the Vector Titration, a resting awake tidal volume determination will be conducted. The participant will be asked to sit in a chair for 30 minutes with the mask, awake, and quietly breathing. Participants will breathe on the device that is manually pressure titrated to the starting tidal volume calculation using 8 ml/kg of ideal body weight (Table 1). After 5 minutes of breathing on the device with the stable target tidal volume, a Borg Scale will be used to assess the patient's level of breathing comfort. This evaluation will continue until the participant's pressure support is manually titrated to the stable target tidal volume that is equivalent to 9 ml/kg and 10 ml/kg of the participant's ideal body weight. The setting that provided the most optimal Borg Scale rating will be the setting used for the study. If optimal tidal volume cannot be achieved after 10 minutes at 10ml/kg of ideal body weight, the participant will be then transitioned to the AVAPS titration protocol.

